4.5.9 Patient Daily Symptom Diary

Patients will use paper diaries to record symptom data ([Nicholson et al. 2000](#); [Treanor et al. 2000](#)) ([Appendix 6](#)). The investigator staff will provide the paper diary and instructions for completing the symptom diary. The purpose of the diary is to record

any symptoms of influenza-like illness, symptom relief medications and temperature (*oral*). The symptom diary card, symptom relief medications and temperature should be completed two times daily: when a patient first wakes up in the morning (before getting out of bed) and ~12 hours later up to Day 14 or until resolution of symptoms (defined as a total symptom score of 0–1 for 24 hours without use of symptom relief medications). Temperature should be taken before administration of acetaminophen/paracetamol and/or NSAIDs (see Section 4.4.1 for permitted medications). Patients should be encouraged to stay consistent with the diary schedule and sites should check that patients are able to take their temperature properly. Day 1 entry will be completed within 6 hours prior to start of study infusion.

Data from paper diaries will be entered into the EDC system by site staff.

4.6 PATIENT, TREATMENT, STUDY, AND SITE DISCONTINUATION

4.6.1 Patient Discontinuation

Patients have the right to voluntarily withdraw from the study at any time for any reason. In addition, the investigator has the right to withdraw a patient from the study at any time. Reasons for withdrawal from the study may include, but are not limited to, the following:

- Patient withdrawal of consent at any time
- Any medical condition that the investigator or Sponsor determines may jeopardize the patient's safety if he/she continues in the study
- Investigator or Sponsor determines it is in the best interest of the patient

Every effort should be made to obtain information on patients who withdraw from the study. The primary reason for withdrawal from the study should be documented on the appropriate eCRF. However, patients will not be followed for any reason after consent has been withdrawn. Patients who withdraw/discontinue/are lost to follow-up may not be replaced.

4.6.2 Study Treatment Discontinuation

Patients must discontinue study treatment during infusion if they experience any of the following:

- Life-threatening infusion-related reactions

The primary reason for study treatment discontinuation should be documented on the appropriate eCRF.

The IMC and SOC may recommend to permanently discontinue further dosing for all patients within one or all study arms in the event of a general safety concern.

4.6.3 Study and Site Discontinuation

The Sponsor has the right to terminate this study at any time. Reasons for terminating the study may include, but are not limited to, the following:

- The incidence or severity of adverse events in this or other studies indicates a potential health hazard to patients.
- Patient enrollment is unsatisfactory.

The Sponsor will notify the investigator if the Sponsor decides to discontinue the study.

The Sponsor has the right to close a site at any time. Reasons for closing a site may include, but are not limited to, the following:

- Excessively slow recruitment
- Poor protocol adherence
- Inaccurate or incomplete data recording
- Non-compliance with the International Conference on Harmonisation (ICH) guideline for Good Clinical Practice
- No study activity (i.e., all patients have completed *the study* and all obligations have been fulfilled)

4.6.4 Study Completion/Early Discontinuation

Patients who complete all study visits through Day 100 are considered to have completed the study. All patients who discontinue from the study early will be asked to complete all assessments for the *current day*. *If a patient discontinues after Day 7, only a telephone visit is required as the Early Discontinuation visit.* Please see Schedule of *Activities* provided in [Appendix 1](#) for assessments performed at the Study Completion *and* Early Discontinuation visit.

4.7 ASSAY METHODS

Serum concentrations of MHAA4549A (pharmacokinetics) will be measured using validated quantitative immunoassays. ATA in serum will be measured using a validated bridging enzyme-linked immunosorbent assay (ELISA). Samples that are positive for ATA may be further characterized, depending on the safety profile and clinical data.

5. ASSESSMENT OF SAFETY

5.1 SAFETY PLAN

MHAA4549A is not approved and is currently in clinical development. Thus, the entire safety profile is not known at this time. The safety plan for this study is based upon preclinical data and the previous Phase 1 and Phase 2a studies. In addition, the safety plan is designed to ensure patient safety and will include specific eligibility criteria and monitoring assessments as detailed below.

The investigator, in consultation with the Sponsor, is responsible for assuring the safety of study participants who have entered this study and for taking appropriate action concerning any event that seems unusual, even if this event may be considered to be an unanticipated benefit to the study participant. The investigator will be responsible for a clinical assessment of the study participants before discharge from the study, and for the establishment of a discharge plan, if needed.

Administration of MHAA4549A or placebo will be performed in a setting with emergency medical equipment and personnel who are trained to monitor for and respond to medical emergencies. A qualified physician *or medically qualified designee* will be on site during study drug administration for all patients. All patients will be monitored for study drug reactions during administration and for at least 30 minutes after completion of study drug administration.

During the study, the incidence and nature of adverse events, serious adverse events, and laboratory abnormalities will be assessed. An ongoing, blinded review of safety will be carried out by the Medical Monitor and a drug safety scientist. An unblinded review of safety will be performed on an ongoing regular basis by the IMC and SOC as described in the IMC/SOC agreement.

5.1.1 Risks Associated with MHAA4549A

There are no known risks associated with MHAA4549A based on *completed* Phase 1 (GV28916, GV29609) and Phase 2 (GV28985) studies.

5.1.1.1 Immunogenicity

MHAA449A is a monoclonal antibody-based therapeutic. As with any recombinant monoclonal antibody, MHAA4549A may elicit an immune response in patients with the development of antibodies against MHAA4549A. Screening, confirmatory, and characterization assay with appropriate sensitivity and therapeutic tolerance will be employed to assess *the prevalence of pre-existing ATAs to MHAA4549A in all study participants. Post-dosing ATAs to MHAA4549A will be measured in subjects with recurrent influenza infections.*

5.2 SAFETY PARAMETERS AND DEFINITIONS

Safety assessments will consist of monitoring and recording adverse events, including serious adverse events and adverse events of special interest, performing protocol-specified safety laboratory assessments, measuring protocol-specified vital signs, and conducting other protocol-specified tests that are deemed critical to the safety evaluation of the study.

Certain types of events require immediate reporting to the Sponsor, as outlined in Section 5.4.

5.2.1 Adverse Events

According to the ICH guideline for Good Clinical Practice, an adverse event is any untoward medical occurrence in a clinical investigation subject administered a pharmaceutical product, regardless of causal attribution. An adverse event can therefore be any of the following:

- Any unfavorable and unintended sign (including an abnormal laboratory finding), symptom, or disease temporally associated with the use of a medicinal product, whether or not considered related to the medicinal product
- Any new disease or exacerbation of an existing disease (a worsening in the character, frequency, or severity of a known condition), except as described in Section [5.3.5.10](#)
- Recurrence of an intermittent medical condition (e.g., headache) not present at baseline
- Any deterioration in a laboratory value or other clinical test (e.g., ECG, X-ray) that is associated with symptoms or leads to a change in study treatment or concomitant treatment or discontinuation from study drug
- Adverse events that are related to a protocol-mandated intervention, including those that occur prior to assignment of study treatment (e.g., screening invasive procedures such as biopsies)

Adverse events will be monitored throughout the entire study (enrollment through Day 100 or Early Discontinuation).

5.2.2 Serious Adverse Events (Immediately Reportable to the Sponsor)

A serious adverse event is any adverse event that meets any of the following criteria:

- Is fatal (i.e., the adverse event actually causes or leads to death)
- Is life threatening (i.e., the adverse event, in the view of the investigator, places the patient at immediate risk of death)

This does not include any adverse event that had it occurred in a more severe form or was allowed to continue might have caused death.

- Requires or prolongs inpatient hospitalization (see *Section 5.3.5.11*)
- Results in persistent or significant disability/incapacity (i.e., the adverse event results in substantial disruption of the patient's ability to conduct normal life functions)
- Is a congenital anomaly/birth defect in a neonate/infant born to a mother exposed to study drug
- Is a significant medical event in the investigator's judgment (e.g., may jeopardize the patient or may require medical/surgical intervention to prevent one of the outcomes listed above)

The terms "severe" and "serious" are not synonymous. Severity refers to the intensity of an adverse event (e.g., rated as mild, moderate, or severe, or according to DAIDS Table for Grading the Severity of Adult and Pediatric Adverse Events; see Section 5.3.3 and Appendix 4); the event itself may be of relatively minor medical significance (such as severe headache without any further findings).

Severity and seriousness need to be independently assessed for each adverse event recorded on the eCRF.

Serious adverse events are required to be reported by the investigator to the Sponsor immediately (i.e., no more than 24 hours after learning of the event; see Section 5.4.2 for reporting instructions).

5.2.3 Adverse Events of Special Interest (Immediately Reportable to the Sponsor)

Adverse events of special interest are required to be reported by the investigator to the Sponsor immediately (i.e., no more than 24 hours after learning of the event; see Section 5.4.2 for reporting instructions). Adverse events of special interest for this study include the following:

- Cases of potential drug-induced liver injury that include an elevated ALT or AST in combination with either an elevated bilirubin or clinical jaundice, as defined by Hy's law (see Section 5.3.5.7)
- Suspected transmission of an infectious agent by the study drug, as defined below
 - Any organism, virus, or infectious particle (e.g., prion protein transmitting transmissible spongiform encephalopathy), pathogenic or non-pathogenic, is considered an infectious agent. A transmission of an infectious agent may be suspected from clinical symptoms or laboratory findings that indicate an infection in a patient exposed to a medicinal product. This term applies only when a contamination of the study drug is suspected.
- Adverse events associated with suspected cases of infusion-related reactions (IRR) which occur within 24 hours of study drug administration and may show the following signs and symptoms (for guidance on reporting adverse events associated with IRR, see Section 5.3.5.1)
 - Fever and/or shaking chills
 - Flushing and/or itching
 - Alterations in heart rate and blood pressure
 - Dyspnea or chest discomfort
 - Back or abdominal pain
 - Nausea, vomiting, and/or diarrhea
 - Various types of skin rashes
 - Anaphylaxis

- Anaphylaxis due to IV drugs most often presents with the following signs and symptoms:
 - Cutaneous symptoms: flushing, itching, urticarial, and/or angioedema (usually of face, eyelids, or lips)
 - Respiratory symptoms: repetitive cough, sudden nasal congestion, shortness of breath, chest tightness, wheeze, sensation of throat closure or choking, and/or change in voice quality due to laryngeal edema
 - Cardiovascular symptoms: faintness, tachycardia (or less often bradycardia), tunnel vision, chest pain, hypotension, sense of impending doom, and/or loss of consciousness
 - Gastrointestinal symptoms: nausea, vomiting, abdominal cramping, and diarrhea

5.3 METHODS AND TIMING FOR CAPTURING AND ASSESSING SAFETY PARAMETERS

The investigator is responsible for ensuring that all adverse events (see Section 5.2.1 for definition) are recorded on the Adverse Event eCRF and reported to the Sponsor in accordance with instructions provided in this section and in Sections 5.4, 5.5, and 5.6.

For each adverse event recorded on the Adverse Event eCRF, the investigator will make an assessment of seriousness (see Section 5.2.2 for seriousness criteria), severity (see Section 5.3.3), and causality (see Section 5.3.4).

5.3.1 Adverse Event Reporting Period

Investigators will seek information on adverse events at each patient contact. All adverse events, whether reported by the patient or noted by study personnel, will be recorded in the patient's medical record and on the Adverse Event eCRF.

After informed consent has been obtained **but prior to initiation of study drug**, only serious adverse events caused by a protocol-mandated intervention (e.g., invasive procedures such as biopsies, discontinuation of medications) should be reported (see Section 5.4.2 for instructions for reporting serious adverse events).

After initiation of study drug, all adverse events will be reported until study *completion* at the Day 100 visit or until an Early Discontinuation visit. After this period, the investigator should report any serious adverse events that are believed to be related to prior study drug treatment (see Section 5.6).

5.3.2 Eliciting Adverse Event Information

A consistent methodology of non-directive questioning should be adopted for eliciting adverse event information at all patient evaluation timepoints. Examples of non-directive questions include the following:

"How have you felt since your last clinic visit?"

"Have you had any new or changed health problems since you were last here?"

5.3.3 Assessment of Severity of Adverse Events

Investigators will seek information on adverse events and serious adverse events at each patient contact. All adverse events, and serious adverse events, whether reported by the patient or noted by authorized study personnel, will be recorded.

The adverse event grading (severity) scale in the DAIDS v1.0 will be used for assessing adverse event severity (see [Table 3](#)).

Table 3 Adverse Event Grading (Severity) Scale

Parameter	Grade 1 Mild	Grade 2 Moderate	Grade 3 Severe	Grade 4 Potentially Life-Threatening
Estimating Severity Grade				
Clinical adverse events NOT identified elsewhere in this DAIDS Adverse Event Grading Table	Symptoms causing no or minimal interference with usual social and functional activities	Symptoms causing greater than minimal interference with usual social and functional activities	Symptoms causing inability to perform usual social and functional activities	Symptoms causing inability to perform basic self-care functions OR Medical or operative intervention indicated to prevent permanent impairment, persistent disability, or death

DAIDS= Division of Acquired Immunodeficiency Syndrome.

5.3.4 Assessment of Causality of Adverse Events

Investigators should use their knowledge of the patient, the circumstances surrounding the event, and an evaluation of any potential alternative causes to determine whether an adverse event is considered to be related to the study drug, indicating "yes" or "no" accordingly. The following guidance should be taken into consideration (see also [Table 4](#)):

- Temporal relationship of event onset to the initiation of study drug

- Course of the event, with special consideration of the effects of dose reduction, discontinuation of study drug, or reintroduction of study drug (as applicable)
- Known association of the event with the study drug or with similar treatments
- Known association of the event with the disease under study
- Presence of risk factors in the patient or use of concomitant medications known to increase the occurrence of the event
- Presence of non-treatment-related factors that are known to be associated with the occurrence of the event

Table 4 Causal Attribution Guidance

Is the adverse event suspected to be caused by the study drug on the basis of facts, evidence, science-based rationales, and clinical judgment?	
YES	There is a plausible temporal relationship between the onset of the adverse event and administration of the study drug, and the adverse event cannot be readily explained by the patient's clinical state, intercurrent illness, or concomitant therapies; and/or the adverse event follows a known pattern of response to the study drug; and/or the adverse event abates or resolves upon discontinuation of the study drug or dose reduction and, if applicable, reappears upon re-challenge.
NO	An adverse event will be considered related, unless it fulfills the criteria specified below. Evidence exists that the adverse event has an etiology other than the study drug (e.g., pre-existing medical condition, underlying disease, intercurrent illness, or concomitant medication); and/or the adverse event has no plausible temporal relationship to administration of the study drug (e.g., cancer diagnosed 2 days after first dose of study drug).

5.3.5 Procedures for Recording Adverse Events

Investigators should use correct medical terminology/concepts when recording adverse events on the Adverse Event eCRF. Avoid colloquialisms and abbreviations.

Only one adverse event term should be recorded in the event field on the Adverse Event eCRF.

5.3.5.1 Infusion-Related Reactions

Adverse events that occur during or within 24 hours after study drug administration should be captured as individual signs and symptoms on the Adverse Event eCRF rather than an overall diagnosis (e.g., record dyspnea and hypotension as separate events rather than a diagnosis of infusion-related reaction or anaphylactic reaction).

5.3.5.2 Diagnosis versus Signs and Symptoms

For adverse events other than infusion-related reactions (see Section 5.3.5.1), a diagnosis (if known) should be recorded on the Adverse Event eCRF rather than individual signs and symptoms (e.g., record only liver failure or hepatitis rather than jaundice, asterixis, and elevated transaminases). However, if a constellation of signs

and/or symptoms cannot be medically characterized as a single diagnosis or syndrome at the time of reporting, each individual event should be recorded on the Adverse Event eCRF. If a diagnosis is subsequently established, all previously reported adverse events based on signs and symptoms should be nullified and replaced by one adverse event report based on the single diagnosis, with a starting date that corresponds to the starting date of the first symptom of the eventual diagnosis.

5.3.5.3 Adverse Events That Are Secondary to Other Events

In general, adverse events that are secondary to other events (e.g., cascade events or clinical sequelae) should be identified by their primary cause, with the exception of severe or serious secondary events. A medically significant secondary adverse event that is separated in time from the initiating event should be recorded as an independent event on the Adverse Event eCRF. For example:

- If vomiting results in mild dehydration with no additional treatment in a healthy adult, only vomiting should be reported on the eCRF.
- If vomiting results in severe dehydration, both events should be reported separately on the eCRF.
- If a severe gastrointestinal hemorrhage leads to renal failure, both events should be reported separately on the eCRF.
- If dizziness leads to a fall and consequent fracture, all three events should be reported separately on the eCRF.
- If neutropenia is accompanied by an infection, both events should be reported separately on the eCRF.

All adverse events should be recorded separately on the Adverse Event eCRF if it is unclear as to whether the events are associated.

5.3.5.4 Persistent or Recurrent Adverse Events

A persistent adverse event is one that extends continuously, without resolution, between patient evaluation timepoints. Such events should only be recorded once on the Adverse Event eCRF. The initial severity (intensity or grade) of the event will be recorded at the time the event is first reported. If a persistent adverse event becomes more severe, the most extreme severity should also be recorded *on the Adverse Event eCRF. Details regarding any increases or decreases in severity will be captured on the Adverse Event Intensity or Grade Changes eCRF. If the event becomes serious, it should be reported to the Sponsor immediately (i.e., ≤24 hours after learning that the event became serious; see Section 5.4.2 for reporting instructions). The Adverse Event eCRF should be updated by changing the event from "non-serious" to "serious," providing the date that the event became serious, and completing all data fields related to serious adverse events.*

A recurrent adverse event is one that resolves between patient evaluation timepoints and subsequently recurs. Each recurrence of an adverse event should be recorded as a separate event on the Adverse Event eCRF.

5.3.5.5 Abnormal Laboratory Values

Not every laboratory abnormality qualifies as an adverse event. A laboratory test result must be reported as an adverse event if it is verified by a repeat assessment and meets any of the following criteria:

- Is accompanied by clinical symptoms
- Results in a change in study treatment (e.g., dosage modification, treatment interruption, or treatment discontinuation)
- Results in a medical intervention (e.g., potassium supplementation for hypokalemia) or a change in concomitant therapy
- Is clinically significant in the investigator's judgment

It is the investigator's responsibility to review all laboratory findings. Medical and scientific judgment should be exercised in deciding whether an isolated laboratory abnormality should be classified as an adverse event. Investigators should promptly repeat any abnormal assessment or clinically significant laboratory result. Only those findings that remain clinically significant upon a repeat assessment will be considered adverse events.

If a clinically significant laboratory abnormality is a sign of a disease or syndrome (e.g., alkaline phosphatase and bilirubin $5 \times$ ULN associated with cholestasis), only the diagnosis (i.e., cholestasis) should be recorded on the Adverse Event eCRF.

If a clinically significant laboratory abnormality is not a sign of a disease or syndrome, the abnormality itself should be recorded on the Adverse Event eCRF, along with a descriptor indicating if the test result is above or below the normal range (e.g., "elevated potassium," as opposed to "abnormal potassium"). If the laboratory abnormality can be characterized by a precise clinical term per standard definitions, the clinical term should be recorded as the adverse event. For example, an elevated serum potassium level of 7.0 mEq/L should be recorded as "hyperkalemia."

Observations of the same clinically significant laboratory abnormality from visit to visit should only be recorded once on the Adverse Event eCRF (see Section 5.3.5.4 for details on recording persistent adverse events).

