5.3.5.6 Abnormal Vital Sign Values

Not every vital sign abnormality qualifies as an adverse event. A vital sign result must be reported as an adverse event if it is verified by a repeat assessment and meets any of the following criteria:

- Is accompanied by clinical symptoms

- Results in a change in study treatment (e.g., dosage modification, treatment interruption, or treatment discontinuation)
- Results in a medical intervention or a change in concomitant therapy
- Is clinically significant in the investigator's judgment

It is the investigator's responsibility to review all vital sign findings. Medical and scientific judgment should be exercised in deciding whether an isolated vital sign abnormality should be classified as an adverse event.

If a clinically significant vital sign abnormality is a sign of a disease or syndrome (e.g., high blood pressure), only the diagnosis (i.e., hypertension) should be recorded on the Adverse Event eCRF.

Observations of the same clinically significant vital sign abnormality from visit to visit should only be recorded once on the Adverse Event eCRF (see Section 5.3.5.4 for details on recording persistent adverse events).

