5.3.5.7 Abnormal Liver Function Tests

The finding of an elevated ALT or AST ($>3 \times \text{ULN}$) in combination with either an elevated total bilirubin ($>2 \times \text{ULN}$) or clinical jaundice in the absence of cholestasis or other causes of hyperbilirubinemia is considered to be an indicator of severe liver injury (as defined by Hy's law). Therefore, investigators must report as an adverse event the occurrence of either of the following:

- Treatment-emergent ALT or AST $>3 \times \text{ULN}$ in combination with total bilirubin $>2 \times \text{ULN}$
- Treatment-emergent ALT or AST $>3 \times \text{ULN}$ in combination with clinical jaundice

The most appropriate diagnosis or (if a diagnosis cannot be established) the abnormal laboratory values should be recorded on the Adverse Event eCRF (see Section 5.3.5.1) and reported to the Sponsor immediately (i.e., no more than 24 hours after learning of the event), either as a serious adverse event or an adverse event of special interest (see Section 5.4.2).

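### Section 5.3.5.5 lets a symptomatic or treated laboratory abnormality that normalises on repeat escape adverse event recording, contradicting 5.2.1, 5.3.5.7 and its own intervention criterion

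*Combined protocol and SAP*

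**What the plan says.** Section 5.3.5.5 lists four criteria for reporting a laboratory result as an adverse event: accompanying symptoms, a change in study treatment, a medical intervention or change in concomitant therapy, and clinical significance in the investigator's judgment. All four apply only "if it is verified by a repeat assessment and meets any of the following criteria". The next paragraph asks for a prompt repeat and ends with the restrictive sentence: "Only those findings that remain clinically significant upon a repeat assessment will be considered adverse events".

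Section 5.3.5.6 has the same structure for vital signs ("A vital sign result must be reported as an adverse event if it is verified by a repeat assessment", plus one of four criteria) but no restrictive sentence.

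Other sections set no repeat condition:
- 5.2.1 counts as an adverse event "Any unfavorable and unintended sign (including an abnormal laboratory finding), symptom, or disease temporally associated with the use of a medicinal product". It also counts a deterioration in a laboratory value or other test that is "associated with symptoms or leads to a change in study treatment or concomitant treatment or discontinuation from study drug".
- 5.3.5.7, on raised ALT or AST combined with raised bilirubin or jaundice, says "investigators must report as an adverse event the occurrence of either of the following" and requires notification within 24 hours.
- 5.2.3 lists "Alterations in heart rate and blood pressure" among infusion-reaction signs for immediate reporting. 5.3.5.1 has events within 24 hours of dosing recorded as individual signs, with hypotension as an example.

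**The concern.** A repeat test shows whether an isolated, unexpected value is real. It is a poor test of whether an event happened when the patient had symptoms or was treated, because a normal repeat may only mean that the problem resolved or the treatment worked. Section 5.3.5.5 applies one condition to both situations.

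Incidence, nature and severity of adverse events form one component of the primary outcome in 3.4.1, so an unclear definition affects what is counted there. It also reaches further. Section 5.2.2 defines a serious adverse event as an adverse event meeting further criteria, the Safety Monitoring Committee reviews blinded adverse events (3.1.3), and several stopping rules in 3.1.4 are framed in terms of adverse or serious adverse events. A finding judged not to be an adverse event may miss those steps. No section says which rule prevails, so one site may follow 5.2.1 and another 5.3.5.5 for the same clinical picture.

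**Working it through.** **1. Logical form.** The reporting sentence in 5.3.5.5 is: repeat verifies AND (symptoms OR change in study treatment OR intervention OR judged significant). The restrictive sentence makes continued clinical significance on repeat a necessary condition. A finding that meets any of the first three criteria but is normal on repeat fails both. Section 5.3.5.6 has the first sentence only: it says when reporting is mandatory, not when an event is excluded.

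**2. The rules side by side, each finding taken as normal on repeat.**

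| Finding | 5.3.5.5 or 5.3.5.6 | Other text |
|---|---|---|
| Laboratory change with symptoms | Not an adverse event (5.3.5.5) | Adverse event (5.2.1) |
| Low potassium, supplemented | Not an adverse event by the restrictive sentence, although potassium supplementation is the section's own example of a qualifying intervention | Adverse event (5.2.1, change in concomitant treatment) |
| ALT or AST >3 × ULN with bilirubin >2 × ULN | Not an adverse event (5.3.5.5) | Must be reported on occurrence (5.3.5.7) |
| Blood pressure fall during infusion | Reporting not mandatory, but not excluded (5.3.5.6) | Infusion-reaction sign, recorded individually (5.2.3, 5.3.5.1) |

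The first three rows are contradictions. The fourth is a tension.

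**3. What is lost.** Section 3.4.1 names graded clinical laboratory abnormalities beside adverse events. Section 6.4 identifies out-of-range laboratory values and summarises vital-sign changes with no repeat filter. The loss is therefore from the adverse event component. The cover is incomplete: 6.4 specifies toxicity-grade summaries for adverse events but summary statistics only for selected laboratory data.

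**4. Relevance of laboratory events.** In the Phase 2a tally in 1.2.2.3, ALT, AST and amylase elevations were 26 of 33 events on MHAA4549A (26/33 = 78.8%) and 15 of 25 on placebo or oseltamivir (15/25 = 60%). That tally covers 33 + 25 = 58 of 207 treatment-emergent events. It shows that such findings are common in infected subjects in all groups. It does not show how many would fail a repeat.

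**5. Scale under an assumption.** Table 5 in 6.1 uses n = 40 and P(at least 1) = 1 − (1 − p)^40. At p = 5% this gives 1 − 0.95^40 = 87.2%, matching the stated 87%; P(at least 2) = 60.1%, matching 60%. The documents give no share c of true laboratory events confirmed on repeat, so c is assumed. The recordable rate becomes p × c:

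| c | p × c at p = 5% | P(at least 1), n = 40 |
|---|---|---|
| 1 | 5% | 87.2% |
| 0.9 | 4.5% | 84.2% |
| 0.75 | 3.75% | 78.3% |
| 0.5 | 2.5% | 63.7% |

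This applies to laboratory events on the adverse event form only. Symptoms recorded in their own right are unaffected.

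**The case against.** The strongest defence is that verification naturally means checking that a value is real, and that 5.3.5.5 asks for a prompt repeat, which may come before any correction takes effect. Its potassium example shows that treated findings were meant to count, and 5.3.5.7 reads as a specific rule overriding a general one. Confirming isolated abnormalities is also a reasonable design choice. The last point stands, and the fix keeps it. The others describe a sensible intention, but the restrictive sentence has no exception and no text gives 5.3.5.7 or 5.2.1 precedence.

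A reader might infer more than the documents support:
- *Loss from the whole primary outcome.* Sections 3.4.1 and 6.4 keep laboratory abnormalities and vital-sign changes in view whatever their adverse event status.
- *Transient vital-sign changes are excluded.* Section 5.3.5.6 lacks the restrictive sentence and leaves isolated abnormalities to judgment, while 5.2.3 and 5.3.5.1 cover infusion-reaction signs.
- *Bias toward no difference from placebo through lost infusion effects.* Appendix 1 schedules no post-dose safety chemistry or haematology before Day 3, so the laboratory rule hardly touches infusion-timed effects. Section 1.3 reports no infusion-related reactions to date. The rule is the same in all arms and is applied by blinded staff.
- *Day 7 findings can never be confirmed.* The prompt-repeat instruction and the unscheduled-visit column, with optional haematology and chemistry, largely answer this.

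**Conclusion.** The contradiction is real and should be corrected. For laboratory findings with symptoms, a treatment change or an intervention, 5.3.5.5 as written denies adverse event status after a normal repeat, while 5.2.1, 5.3.5.7 and the section's own third criterion point the other way. For vital signs the text is in tension with 5.2.3 and 5.3.5.1, no more.

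The consequence is possible under-recording and inconsistent classification between sites, in the adverse event component only. Its size cannot be derived from the documents, and the range shown rests wholly on the assumed confirmed share. The conclusion assumes that sites apply the restrictive sentence literally; a site that reads it as a check for spurious values would lose little. No direction of bias between arms is claimed. No sample size or probability stated in the plan is wrong because of this point.

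**What to change.** Amend the wording as follows:

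1. In 5.3.5.5 and 5.3.5.6, require repeat verification only for an isolated abnormality reported solely on investigator judgment (the fourth criterion). Remove it for symptoms, change in study treatment, and intervention or change in concomitant therapy.
2. Restrict the final sentence of the investigator-responsibility paragraph in 5.3.5.5 to that fourth criterion.
3. State that 5.2.1, 5.2.3, 5.3.5.1 and 5.3.5.7 take precedence, so that events meeting them are recorded without waiting for a repeat, a documented laboratory error excepted. Add that 5.2.1's general mention of abnormal laboratory findings does not by itself override the repeat for isolated abnormalities; otherwise the precedence statement would cancel item 1.

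The cost is protocol text and site training, with no new test or visit. The downside is that a few more transient adverse events will be recorded in all arms.
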